Intervention Counseling Sessions: Digital auto recordings containing confidential information about the participants will also be collected for protocol quality control and participants' safety monitoring. Counselors, employed by each of the hospitals, will deliver the intervention via in-person or over the phone and will audio record their counseling sessions with participants. Audio-recordings will be saved electronically with the numeric code used as the only identifier of the participant. The audio-recorded sessions will be reviewed by [name], [name], and [name], licensed clinical supervisors and IRB trained. The participants' names, last names, numeric study code, and contact information will be kept in our password-protected REDCap database. Audio-recordings will be shared electronically with the clinical supervisors, and with the PI and DSMB members HIPPA Compliant, University MS ONE Drive for Business account where they will be made accessible upon request.

E. Potential Benefits of the Proposed Research to Human Subjects and Others

To LC and HNC patients and their caregivers: Patients and caregivers who will receive the stepped-care intervention would benefit from receiving services that are targeted to their distress (i.e., mild, moderate, severe), which has the potential to improve their mental health wellbeing, along with potential gains in coping self-efficacy and decreased stress among other gains. Any risk involved in the study, such as temporary distress, may be outweighed by improvements to mental health needs.

To society: There is a dire need to provide underserved LC and HNC patients and their caregivers with mental health support. If successful, the intervention could improve mental health outcomes, patients and caregivers' satisfaction with care, QoL, and caregiver burden. It may also provide other institutions with a cost-effective method to help underserved cancer patients receive mental health treatment. Thus, information gained is likely to outweigh any minimal risks (e.g., temporary psychological distress).

Funding

PCORI (154219) AD-1511-33395. Funding of this study will not pay for medical or mental health treatment for the participants. Participants are responsible for their own standard medical or mental health care. Participants will be given a \$25.00 compensation for taking the time to answer the measures during the four total assessment points, thus, each participant randomized to condition will be paid a total of \$100. Participants who are not randomized will only answer the "baseline measures" and will only receive \$25.00 for that assessment point. Participants will not be paid for participating in the study, the RCT, or the Counseling sessions provided through the stepped-care intervention.

Special Consent Issues

There are no consent issues involving special populations such as prison inmates, persons with cognitive disabilities, homeless, or minors.

Examinations, laboratory tests, and procedures

Not applicable

Biological Specimens/Genetic Testing

This study does not involve collection of specimens or genetic testing.

F. Potential Scientific Problems

Potential limitations to this study include: researcher bias, participants bias, and generalizability. However, the oversight of the development, implementation, and evaluation of the study protocol,

intervention, and conduct of RCT by a group of "Patient and Caregiver Stakeholders (PCS)," Clinician Stakeholders, and the DSMB will ensure that any bias introduce by the research team leadership and staff are minimized. The researchers will ensure that they standardize the interpretation of results during data analysis in order to reduce the impact of researcher bias. Some of our participants are cancer patients under distress and in need of services who might perceive the intervention to be more beneficial than under ordinary circumstances. Self-report measures might also lead to recall bias in reporting. Finally, we cannot generalize our findings to the overall LC and HNC patient and caregiver population because the focus is on medically underserved LC and HNC cancer patients and caregivers.

G. Data Analysis Plan: An individual-level RCT design will assess the effects of the *stepped care intervention* condition compared to *enhanced usual care* condition on distress and adaptive coping skills.

Sample size and power analysis: We estimated minimum effect sizes detectable for different power specifications for various sample sizes. Our target sample size for analyses is 290 patients and 290 caregivers (145 per arm) but we will recruit an initial sample of 222 patients and 222 caregivers (222 per arm) to allow for variability due to 24-34% attrition, based on attrition rates in meta-analyses ⁸⁸ and in our studies. ^{57, 59} If we had a smaller number of participants or if attrition was higher, we would need a minimum of 110 dyads per arm to still be able to detect small to moderate effect sizes. Power is assumed to detect a time by treatment interaction within the proposed repeated measures design. Correlation of measures across time points (rho) was specified as moderate (.4), although sensitivity analyses examined the minimum detectable effect size at alternative specifications of rho and still allow small to moderate effects. Power calculations are for 3 outcomes through a Bonferroni reduction of the significance level to alpha = 0.05/3 = 0.0167. The study is designed to minimize contamination between intervention and control groups (e.g., randomizing both patients and their caregivers to the same group, referrals based on usual care practices). Nevertheless, based on Torgerson, we conservatively powered the study to detect a smaller effect than anticipated in the event of potential contamination.

Analysis approach: Using an intent-to-treat (ITT) approach, primary and secondary outcomes will be analyzed with *linear mixed models* comparing the two groups (*stepped care intervention, usual care*) in patients and caregivers separately.

Data aggregation, distributional assumptions, missing data, and attrition: Maximum likelihood techniques will include participants with incomplete data without need for imputation. This technique is robust under certain conditions such that group comparisons will not be biased as long as missing data is ignorable. ^{90, 91} In addition, we will conduct sensitivity analyses to examine the effect of departures from key assumptions (e.g., similarity between groups) made in the main analysis and to help determine effects of missing data. ^{92, 93} This approach will allow us to determine whether the significance of the main analysis was maintained in all sensitivity analyses or was changed in a limited or large number of sensitivity analyses. If this is the case, then separate analyses of only those participants who complete the study will be conducted. To prevent missing data, participants will be administered the measures by research assistants trained on their proper administration. Such an approach is more appropriate for low-literacy populations and maximizes the completion of the measures. During the course of the trial, monthly reports will be generated summarizing recruitment/accrual and completeness of follow-up to allow collaborating sites to proactively follow-up with participants in a timely manner.

Verification of Randomization, Inclusion of Covariates, and Stratification: Preliminary analyses will check for baseline differences between groups. By using a RCT, we seek to have groups that will be as similar as possible, even in terms of unknown covariates, allowing us to isolate the effect of the intervention.

Should differences remain, we will co-vary variables that are correlated with the outcome and that differ by group. Because we are recruiting from four sites, we will verify that site has no impact on outcomes, either as a main effect or through interactions with treatment. Given block randomization, no differences are expected, particularly no differences in treatment response by site, though we are powered to detect differences between the four sites as low as f=.18 (Cohen's d=.36). In addition to site, responses to the intervention may be further stratified by tumor site (LC vs. HNC) or stage of diagnosis; thus, we will use a block randomization and adjust for imbalance by these variables. We will introduce *fixed effects* to account for stratified randomization in our primary analysis.

Analytic Strategy: Primary and secondary outcomes will be analyzed with linear mixed models comparing the two groups (stepped care intervention, enhanced usual care) in patients and caregivers separately. An alpha level of 0.05 (alpha = 0.05/3 for primary outcomes) will be used to evaluate the a priori planned comparisons. Two-tailed tests will help to detect differences between groups. The study is powered for testing the hypothesis of no group differences in change over the four time points. The software SAS PROC MIXED will be used. 94 For hypotheses addressing group differences for patients and separately for caregivers, outcomes will be evaluated with the same design: 2 groups (stepped care intervention, enhanced usual care) over 4 times (prior to randomization, 6 weeks, 3 months, 6 months). Mixed models will specify group and time and their interaction as fixed effects and subject as a random effect, where subject is assumed independently normally distributed with mean 0 and variance independent of the random errors. A significant group by time interaction is hypothesized, where those in the stepped care intervention are expected to improve to a greater degree than those in the enhanced usual care group. Planned comparisons of group differences at each time point will be conducted in the event of a significant interaction effect. In analyses of caregivers, the model of distress will include the caregiver's age and gender as covariates, as they have been found to be related to their distress; we will also investigate inclusion of patient distress, physical and QoL as covariates. The patient model of distress will include no a priori covariates, but we will explore inclusion of caregiver distress.

Heterogeneous Treatment Effects: To assess how the heterogeneity of the sample may impact treatment effects, a descriptive analysis will be conducted to estimate treatment effects with *standard errors* for important subgroups determined by levels of sex, ethnicity, tumor site (LC vs. HNC), stage (I-II vs. III-IV), hospital site and primary language (English vs. Spanish). Analyses will be based on mixed models for each subgroup. A second analysis will add each factor separately to mixed models for the entire sample. We plan to report on the pre-specified analyses and any post-hoc analyses of subgroups and outcomes analyzed to contribute to the trial's utility and interpretability for implementation and dissemination.

H. Summary of Knowledge to be Gained

Participating in an intervention that improves symptoms of distress (depression and anxiety) may help patients and their caregivers benefit from much needed assistance compared to not receiving support. By comparing the *stepped-care intervention* to usual care practices, the information gleaned from the results would demonstrate whether or not an evidence-based intervention targeted to patients' and caregivers' mental health needs would produce better patient-centered outcomes than usual care. Any temporary discomfort or time spent during the intervention is considered minimal compared to how the information gained from the study could affect future underserved LC and HNC patients. If successful and scalable, the study would not only improve access and services for underserved LC and HNC patients, but it would contribute information on effective interventions to reduce health disparities.

REFERENCES CITED

- 1. American Cancer Society. Cancer Facts & Figures. Atlanta, GA: American Cancer Society; 2015. Access March 2, 2015.
- 4. Singh, B. Rehabilitation and Quality of Life Assessment in Head and Neck Cancer. In: Shah JP, Patel SG, eds. *Cancer of the Head and Neck*. Hamilton, Ontario: BC Decker Inc; 2001:467-77.
- 6. Frampton M. Psychological distress in patients with head and neck cancer: review. *Br J Oral Maxillofac Surg*. 2001;39(1):67-70.

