A. Outcome Measures: We will utilize patient-reported outcome (PRO) measures that have been found to be valid and reliable, including with Spanish-speaking populations (see Table 1). To ensure that the measures are appropriate for low-literacy populations, a pilot test was conducted with our patient and caregiver stakeholders and items that were difficult to understand or to answer were simplified. Thus, we will further assess their validity and reliability in our sample. All consented study participants will be compensated \$25 to complete the measures at baseline ("baseline measures"), which will also include sociodemographic questions to determine "randomization inclusion and exclusion criteria." Only participants who are randomized to condition will complete the measures at 6-weeks, 3-months and 6-months from the date they completed the baseline measures and will be compensated \$25 every time.

Table 1. Patient-centered outcomes to be assessed at baseline, 6-weeks, 3-months, and 6-months

	Patients	Caregivers
PRIMARY OUTCOMES		
Depression & Anxiety	Hospital Anxiety and Depression Scale (14 items)	Hospital Anxiety and Depression Scale (14 items)
Depression	PROMIS-Ca Form v1.0 – Depression (30 items)	PROMIS Form v1.0 – Depression (28 items)
Anxiety	PROMIS-Ca Form v1.0— Anxiety (22 items)	PROMIS Form v1.0 – Anxiety (29 items)
Coping	Coping Self-Efficacy (26 items)	Coping Self-Efficacy (26 items)
SECONDARY OUTCOMES		
Health-Related	FACT-Lung Cancer version 4 (36 items)	
Quality of Life	FACT-Head-and-Neck Cancer (27 items)	
Perceived Stress	Perceived Stress Scale (PSS) (10 items)	Perceived Stress Scale (PSS) (10 items)
Caregiving Burden		Zarit Burden Interview (ZBI) (12 items)

The measures package takes about +/- 30 minutes to complete when it is *self-administered online* or via a *hard copy* but about 45 minutes when administered orally in person or over the phone. If a participant is unable to complete the measures online or express preference for a hard copy, they will be:

- (1) Mailed a copy of the measures and ask to return within 15 days of receipt. If after 15 days of the initial online request or if they expressed preference for an oral administration, they will:
- (2) Receive a phone call from a Graduate research assistants (GRA) who will administer the measure to participants by phone. If the GRAs are unable to locate the participants after 3 attempts (including leaving voice messages), they will

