 - e. All patients and caregivers who agree and consent to participate in the study will receive a follow-up letter. The letter will include information based on whether or not the participant is randomized to a study condition, and if the participant is randomized, then he/she will receive a letter based on the step to which he/she was randomized. The letters are as follows: a) Letter to participants not randomized to a study condition, b) Letter to participants in the control condition, c) Letter to participants randomized to Step 1 of the intervention, d) Letter to participants randomized to Step 2 of the intervention, e) Letter to participants randomized to Step 3 of the intervention, f) Letter to participants randomized to Step 4 of the intervention.
 - f. Advertise the study via Social Media sites and instruct recently diagnosed LC or HNC patients and their caregivers to contact the Site Coordinator if interested in the study.
- 2. All recently diagnosed LC and HNC patients and their caregivers will be informed and invited to participate in the study following a series of procedures:
 - a. Site Coordinator will arrange an information meeting with the patient (e.g., scheduled medical visit) to introduce and invite patient (and caregiver if present) to participate.
 - b. If the patient's caregiver is not present, the Site Coordinator will ask for the patient's agreement to contact their caregiver via phone to invite them to participate in the study. The patient will be informed that "dyad" participation is not required but that only one or both of them can participate if desired.
 - c. For caregivers absent at the time of the patient's recruitment, the Site Coordinator will arrange to meet the caregiver to inform and invite them to participate in the study.
- 3. We will consent all recently diagnosed LC and HNC patients who agree to participate in the study
 - a. For patients and caregivers who agree to participate, the Site Coordinator will arrange a time to explain and sign the informed consent (IC). The time to conduct the IC process and sign the IC form could be during the initial recruitment meeting or at another subsequent time if that is more convenient for the patient and/or the caregiver.

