- D. PHI for each participant will be kept unidentified in REDCap,™ to be identified by a numeric study code assigned to the participant upon being consented into the study (only the Site Coordinators as employees of the institutions will have access to identified information). The SRC will only record PHI on the diagnostic criteria (e.g., LC and HNC) from all prescreened individuals. The SRC will also record demographic data (e.g., age, gender, ethnicity, patient) to log recruitment efforts and for the DSMB to evaluate bias in recruitment, and for final analysis to determine demographics of individuals who were not included in the study.
- E. Each participant will be asked to provide, if possible, two phone numbers to deliver to them information related to their participation in the study (e.g., appointment reminders).
- 4. Using information collected from the "baseline measures" we will screen for "randomization inclusion and exclusion criteria," which includes the following criteria:

LC and HNC patients' randomization criteria [information in brackets refers to the question numbers that assess inclusion and exclusion criteria in the sociodemographic survey, attached]

Eligibility criteria:

- a) Recently diagnosed LC and/or HNC (within a month of recruitment date from the date of 1st visit oncology, ENT, or radiation clinic visit/consultation upon pathologic tissue diagnosis [question #14]
- b) LC and/or HNC patients at any stage of diagnosis (Stages 0-IV) [question #15];
- c) Over 18 years old; [question #1];
- d) English and/or Spanish speaking [questions #4];
- e) Medically underserved, as defined by at least one or several of the following:
 - a. Low-income: Below 400% of the 2016 Federal poverty levels 85,87 [question #10];

- b. Uninsured: No health insurance (public or private insurance) [question #9];
- c. Underinsured:
- (c.1) Public insurance (e.g., Medicaid, Medicare exclusive, VA) [question #9];
- (c.2) 10% of annual income on out-of-pocket medical expenses⁸⁶ for individuals below 200% of the 2016 Federal poverty levels [questions #9 and #10].

Exclusion criteria:

- a) Individuals who do not meet eligibility criteria, including individuals who do not speak English or Spanish [at the discretion of the Site Coordinators upon recruitment];
- b) Those who refuse treatment at one of four hospital sites.

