- d) Individuals from vulnerable populations (e.g., inmates [question #29], homeless [question #28], pregnant women [question #2], and those with auditory impairment [at the discretion of the Site Coordinators upon recruitment]). However, individuals who become pregnant or develop auditory impairments after they have been randomized to

study condition may remain in the study until completion. Additionally, individuals on probation will be considered eligible and their participation in the study will not interfere with their requirements of probation.

5. We will randomize participants (patients and caregivers) who meet the "eligibility criteria" and exclude from randomization participants based on the "exclusion criteria."

C. Randomized Controlled Trial (RCT) Design

Population: To estimate the population of participants, we obtained data on the number of patients who have been diagnosed with LC and HNC at DHHA, University of Colorado Hospital, NJH, and St. Mary's in a 3-year period (2012-2014) prior to the grant submission. The 4 sites had a population of about 1,211 LC and HNC patients who would be invited to participate in the study to complete "baseline measures," with about 70% of patients expected to meet criteria as being uninsured or underinsured patients. As **Figure 1** displays, the estimated sample is 848 patients (and 848 of their caregivers) expected to be eligible for randomization.

Participants who meet the "randomization inclusion criteria" will be randomized to condition by the database manager using the REDCap™ software at CU-Denver as follows:

- 1. Block randomization, adjusting for imbalance in patients' tumor site and stage of diagnosis in the analysis, will ensure an equal distribution of patients and caregivers across arms.
- 2. For patients and caregivers who both agree to participate in the study, they will be randomized together to the same condition (either "enhanced usual care" or "stepped-care intervention"). Per "baseline measures" of distress, patients and caregivers randomized to the "stepped-care intervention" will be assign to an intervention step based on their individual distress scores.

Randomization and sample size: Figure 1 shows the participants' random assignment to study condition.

[figure not shown]

Figure 1. The 444 participants expected to be randomized (222 LC and HNC patients and 222 caregivers)

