- Step 3: Coping Skills Training: (PROMIS score 60-69). ⁶³ Participants experiencing moderate levels of distress will receive the *Orientation Session*, the *Self-Help Guide*, and two *Coping Skills Training* sessions with the Counselor. Participants will learn problem-focused and emotion-focused coping strategies, ⁵⁴ and to identify controllable and uncontrollable stressors and how to match them to the appropriate strategy. Participants will practice the strategies between sessions.

Step 4: Cognitive-Behavioral Therapy (CBT): (PROMIS score >70).⁶³ Participants reporting high levels of distress, will receive the *Orientation Session*, the *Self-Help Guide*, two *Coping Skills Training* sessions, and four *CBT sessions*. The Counselor will introduce evidence-based CBT techniques, which focus on modifying the impact of stress via the interpretation of and reactions to stressors (cognitive and emotional reactions) and by correcting cognitive distortions. Participants who are not helped by the intervention or who require specialized treatment will be referred for services at the hospital, although they will continue to be included in the final analyses. If a patient dies, the caregiver may continue participating and will be moved to Step 4 to receive a grief session.

[figure not shown]

Figure 1. Stepped-Care Intervention Conceptual Framework to Assign Participants to a Step. 95

Referral Protocol: Participants (baseline group, enhanced usual care, and stepped-care intervention) will be referred to specialized mental health care if they endorse suicide ideation or substance abuse items during any of the assessment points (baseline, 6-weeks, 3-months and 6-months) or if they voice such issues to the Site Research Coordinator upon enrollment or to the Counselor during the intervention. If participants are not helped by the intervention or require psychiatric medication, they will be referred also to specialized mental health services per protocols already in place at the participating hospitals. During the study's 12-hour training, the Site Coordinators and Counselors will be instructed to follow their institution's protocol for suicidal ideation and other crisis (e.g., intoxication) to make referrals.

D. Description, Risks and Justification of Procedures and Data Collection Tools

Potential Risks

- a) Physical injury No known risks, but if there are risks they are likely to be rare and the magnitude low.

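### Follow-up is timed from each participant's own baseline questionnaire, not from randomisation, and the interval between them has no limit, so time since allocation at a nominal visit is shortened by an uncontrolled lag that can differ within a dyad.

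*Combined protocol and SAP*

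**What the plan says.** - **Time origin.** Section IV.A (Outcome Measures) sets the three follow-up assessments at "6-weeks, 3-months and 6-months from the date they completed the baseline measures and will be compensated". Only randomised participants are to complete them.
- **Order of events.** Section IV.B, item 4, takes the randomisation criteria from the baseline data. The Analytic Strategy in section IV.G describes two groups "over 4 times (prior to randomization, 6 weeks, 3 months, 6 months". Baseline therefore comes before allocation for everyone.
- **Dyads.** Section IV.C states: "For patients and caregivers who both agree to participate in the study, they will be randomized together to the same condition". Section IV.B, item 2, makes dyad participation optional and adds: "For caregivers absent at the time of the patient's recruitment, the Site Coordinator will arrange to meet the caregiver". No deadline is attached.
- **Questionnaire routes.** Section IV.A allows 15 days for return of a mailed package, then telephone attempts, then an approach in person. The last two have no time limit.
- **Use of each visit.** Section IV.A classes outcomes as positive or negative at the assessment points. Section IV.G plans group comparisons at each time if the group-by-time interaction is significant.

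I found no cap on the interval from baseline to randomisation or to the first session, no follow-up visit window, no session calendar, and no rule for a caregiver who joins after the patient has been assessed.

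**The concern.** The model treats 6 weeks, 3 months and 6 months as the same points for everyone. Under the stated rule they are the same only in time since baseline. Time since allocation is shorter by however long screening and joint randomisation took.

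The lag takes time from the intervention. The Mental Health Resource Guide is handed out at enrolment, whereas stepped care cannot start until allocation is known. A longer lag means less of the intervention has been delivered when the 6-week score is taken. The longest course, Step 4, has the most left to deliver: one orientation, two coping sessions and four CBT sessions, seven contacts in all.

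Within a dyad, the member who completed baseline first has had less time since allocation at the same nominal visit. At stake are the size and interpretability of the 6-week comparison and, to a degree that depends on how the effect develops, the power of the group-by-time test.

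**Working it through.** **1. The plan's own figure.** Section IV.C states 90% power for an effect size of 0.38 with 178 analysable participants per arm. Section IV.G gives a two-sided alpha of 0.05/3 = 0.0167. For a two-group comparison with unit SD:

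power = Φ(d·√(n/2) − z) = Φ(0.38 × √89 − 2.394) = Φ(3.585 − 2.394) = 0.883.

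This is within two points of the stated 90%. The match is not unique: 145 per arm at alpha 0.05 gives 0.899. Neither calculation involves the timing rule. The 178 also pools patients and caregivers, who are to be modelled separately, so the powers below show relative change only.

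**2. The lag.** Let B be a member's baseline date and R the dyad's randomisation date. Then L = R − B, and time since allocation at a visit on day t is t − L. For two members with a common R, the difference in exposure is the difference between their baseline dates. A slow questionnaire from the second member lengthens the first member's lag; hence the use of 15 days as an illustration.

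**3. Exposure over a range of assumed lags.** Months are taken as 91 and 182 days. Step 4 contacts assume weekly sessions, which the plan does not state. The two counts place the first contact on the day of randomisation, floor((42 − L)/7) + 1, or a week later, floor((42 − L)/7).

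| L (days) | Days since allocation at 6 weeks | Share at 6 weeks | Share at 3 months | Share at 6 months | Step 4 contacts of 7 by day 42 |
|---|---|---|---|---|---|
| 0 | 42 | 100% | 100% | 100% | 7 or 6 |
| 7 | 35 | 83% | 92% | 96% | 6 or 5 |
| 15 | 27 | 64% | 84% | 92% | 4 or 3 |
| 21 | 21 | 50% | 77% | 88% | 4 or 3 |
| 30 | 12 | 29% | 67% | 84% | 2 or 1 |

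**4. The 6-week contrast, if effect is proportional to exposure (an assumption).** At L = 15, d = 0.38 × 27/42 = 0.24 and power is Φ(0.244 × 9.434 − 2.394) = 0.46, against 0.88 at L = 0. At L = 7 it is 0.72, at L = 21 it is 0.27, and at L = 30 it is 0.09. With half of 178 (89 per arm, one population), power goes from 0.56 at L = 0 to 0.22 at L = 15.

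**5. The group-by-time test.** Take the plan's correlation of 0.4, 178 per arm, three degrees of freedom, and group differences δ at the three follow-up visits. The noncentrality is λ = n/(2 × 0.6) × [Σδ² − (Σδ)²/4].

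- No lag, δ = 0.38 at every visit: λ = 148.3 × (0.4332 − 0.3249) = 16.1, power 0.86.
- Effect proportional to exposure at every visit: power 0.67 at L = 15 and 0.56 at L = 30.
- Only the 6-week effect reduced: power 0.81 at L = 15 and 0.88 at L = 30. It recovers because an effect that emerges late makes the time profile less flat, and the interaction test responds to that.

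The loss for the primary test is therefore not of fixed size, or even of fixed sign.

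**The case against.** Timing visits from baseline is a legitimate choice: it gives everyone equal intervals between measurements. Both arms use the same pre-randomisation clock, so the comparison is not biased. Patients and caregivers are modelled separately, so unequal exposure within a dyad mainly touches the exploratory cross-member covariates. The plan nowhere calls 6 weeks the end of treatment, and with weekly contacts Step 4 would reach day 42 with no lag at all. Step 3's three contacts would be complete by day 42 for lags up to 28 days (21 on the later-start count), and Steps 1 and 2 have one scheduled contact each. Tablet entry (section IV.D) and administration by trained assistants (section IV.G) may keep lags short. All of this stands, and it limits the size of the problem. It does not supply the missing cap on the interval.

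A reader might infer several stronger things that the documents do not support:

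- **That some 6-week scores would be taken before randomisation.** Section IV.A gives follow-up only to randomised participants. A very long lag would make that visit late, missed or almost unexposed. The plan neither shows nor excludes such lags.
- **That dyads are held back for the second member.** This follows if each member's baseline is needed before joint randomisation, but no text says so, and it cannot apply to someone taking part alone.
- **That a third to two thirds of the 6-week effect is lost.** That needs lags of 14 to 28 days and an effect proportional to elapsed time, neither of which is documented.
- **That slow sites would show a false site effect.** Nothing in the documents bears on site-specific delay.

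**Conclusion.** The point holds as a weakness in the scheduling rule. It rests on text: the clock starts at each person's own baseline, baseline precedes allocation, participating dyads are randomised together, and nothing bounds the interval. Exposure at a nominal visit is t − L, and within a dyad it differs by the gap between baseline dates.

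The size cannot be fixed from the documents because L is not given. At the illustrative 15 days the 6-week visit falls 27 days after allocation, while the 6-month visit keeps about 92% of its time. The expected consequence is dilution and noise, concentrated in the 6-week comparison and in Step 4. The power figures depend further on an assumed link between exposure and effect. The change is worth making because it is cheap, not because the primary result is shown to be at risk.

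**What to change.** **Newly enrolled participants.** In section IV.A, time the three follow-up assessments from the date of randomisation, with one date per dyad. State a maximum interval from baseline to randomisation; if it is exceeded, repeat the primary outcome measures before randomising.

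**Participants already enrolled.** Keep the existing schedule. Record days from randomisation to each assessment and to the first intervention contact, and report them by arm and by dyad status. In section IV.G, add a sensitivity mixed model using actual time since randomisation.

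**Cost.** Protocol wording, a change to the REDCap scheduling rule and an occasional repeat of the primary measures. Visits move later by the screening lag, and early and late enrollees will have slightly different visit timing, which the sensitivity model should cover. The change does not remove delay between randomisation and the first session, so that interval should be reported as well.
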